11.2 Treatment Visits

Subjects that did not experience significant pain or skin sensitivity in response to the test spots can receive treatments. Each subject will be enrolled and scheduled for two treatments, three weeks apart and return for a follow-up visit three days after the second treatment for evaluation of the treatment area.

The following procedures and assessments are required at the treatment visits:

Pre-treatment

- Confirm continued eligibility regarding inclusion/exclusion criteria
- Review any changes in medication, health status or AE from last visit
- Assessment of adverse events including a photograph of the affected treatment area if an adverse event occurred
- Assessment of concomitant medications
- Assign randomized treatment (after 1st treatment visit only)
- Apply a topical anesthetic preparation over the treatment areas, if required. (If used, record in the CRF.)

Treatment

No lotion, gel or coupling medium is to be used in this treatment. The distal part of the applicator should be clean and dry before fitting it with a new 160 pins tip. The skin in the treated area should also be cleaned well (for removal of any lotions, make-up residues, topical anesthetic cream, etc.) and patted dry. Hairs that exist in the areas should be shaved off.

- Treatment should be performed while the subject is lying down comfortably; the operator should have easy access to the subject's treatment area.
- Areas of dental crowns, caps, braces, or other metal dental implants may be more sensitive to treatment and the clinician may use dental rolls, gauze or a tongue depressor to isolate the area and make the treatment more comfortable (if the face is treated).
- Treatment of subjects in hair-bearing areas may result in some damage to the follicles and subsequent loss of hair. Avoid the beard area (if face is treated) and other hair growing zones if the patient doesn't wish to have reduction of the hair growth. This treatment may also result in in-grown hairs.
- The applicator should be held perpendicular to and in close contact with the skin.
- Pressing the trigger will release the RF energy to the skin, creating a stamped imprint in a shape and intensity depending on energies.

- The immediate responses, indicative of the desired effect, are erythema and edema in the immediate area of the stamp and possibly also around it. The edema usually appears 1-2 minutes post-treatment and reaches its peak (of up to moderate edema) within 30 minutes. It should be noted that erythema is not easily noticeable, if at all, in darker skin types, so the edema will indicate a more significant effect in these subjects.
- Treatment consists of a single pass over the designated area.
- Unless otherwise instructed, the energy parameters can be modified between the treatment visits, as per the Investigator's discretion.
- It is recommended that throughout the study, that one staff member administer the treatments and another staff member perform the evaluations of the treatment area.

Post Fractional RF Treatment

- Subject Discomfort Assessment recorded on a 100mm visual analogue scale (VAS) immediately post treatment.
- Subject Tolerability Scale immediately post treatment.
- Subjects will receive either the adjuvant combination treatment (SCR Complex™ followed by Bio Cel™ occlusive gel applied to the treatment area) or SOC (no topical applications to treatment for 24 hours post fractional RF treatment).
- Subjects will be asked to complete the Subject Home Tolerability Scale at 24 hours and 72 hours post-treatment
- Subjects will be provided with the Subject Home Instruction Sheet (Appendix B).
- A follow-up telephone call will be made to the subject 24 and 72 hours after the first treatment and 24 hours after the second treatment. Study staff will ask the subject to report on the treatment using the Self-Report Adverse Event Questionnaire (Appendix C) and remind the subject to complete and return to the clinic with their completed Subject Home Tolerability Scale at each visit.

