1. SCHEDULE OF EVENTS

Visit:	Screening & Test Spot	Tx 1¹	Tx 2	FU1
Day:	0	7	21	24
Inclusion/ Exclusion	+			
Informed Consent Form	+			
Demographics, Medical / Medication History, Skin type	+			
Fitzpatrick Wrinkle and Elastosis Scale evaluation	+			+
Test spot	+			
Treatment		+	+	
Subject discomfort assessment (VAS)		+	+	
Subject Self-Report Adverse Event Questionnaire		+ ²	+ ³	+
Subject Tolerability Scale (5-point Likert scale)		+ ²	+ ³	+
Investigator improvement evaluation using GAIS				+
Adverse Events / Concomitant Medications		+	+	+

¹The baseline visit and 1st treatment visit may be scheduled on the same day.

²Telephone call to subject 24 hrs and 72 hrs post first treatment; Subject Tolerability Scale 0; Subject Home Tolerability Scale 24hrs and 72hrs post treatment

³ Telephone call to subject 24 hrs post second treatment; Subject Tolerability Scale 0; Subject Home Tolerability Scale 24hrs post treatment

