9. SUBJECT SELECTION AND WITHDRAWAL

Inclusion Criteria

Subjects must satisfy the following criteria to be enrolled in the study:

1. Male or non-pregnant, non-nursing female at least 21 years of age and less than 75 years of age.
2. Undergoing a dermatological procedure requiring ablation and resurfacing of the facial skin utilizing the Venus Viva™ SR system.

3. Women of child-bearing age are required to be using a reliable method of birth control prior to enrollment and throughout their participation in the study.
4. Able to tolerate the treatment as determined by a test spot application(s).
5. Mentally and physically competent to sign an informed consent document indicating that they understand the purpose and procedures required for the study and are willing to participate.
6. Able and willing to comply with the treatment/follow-up schedule

Exclusion Criteria

Subjects who meet any of the following criteria will be excluded from participation in the study:

1. Superficial metal or other implants in the treatment area.
2. Tattoos, permanent makeup, scars or piercings in the treatment area.
3. Current or past history of significant systemic illness.
4. Any active condition in the treatment area, such as sores, psoriasis, eczema and rash.
5. Subjects with a pacemaker or planned cardioversion in the future.
6. Receiving therapies or medication that may interfere with the study treatment.
7. Any surgical procedure in the treatment area within the last three months or before complete healing.
8. Currently receiving or received within 6 months before the planned start of treatment, an investigational drug / experimental medical device.
9. Any physical or mental condition, as per the investigator's discretion, which may make it unsafe for the subject to participate in this study.

Subject Withdrawal Criteria:

A subject has the right to withdraw from the study at any time, for any reason, without prejudice to her future medical care by the physician or the institution. Should a subject (or the subject's legally authorized representative) decide to withdraw, all efforts will be made to collect and report the final visit observations as thoroughly and timely as possible. Permission to contact subjects for the purpose of determining their status even after participation in the study is complete will not require additional ethics approval.

Subjects may be removed from the study if any one or more of the following events occur:

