11.1 Screening Visit

The following procedures will be performed at the screening visit:

- Written informed consent
- Assign unique identifying number
- Inclusion/exclusion criteria
- Demographics
- Physical examination
- Medical history
- Concomitant medications
- Skin type (Fitzpatrick Scale)
- Wrinkle evaluation (Fitzpatrick Wrinkle and Elastosis Scale)
- Test spot

Test Spot

In order to assess tolerability to treatment, up to three test spots will be performed on the area adjacent to the ear on the side of the neck close to the back (so as it is not visible). Test spots should be based on skin type and desired outcome as per the chart below. The test spots will be used to determine the optimal parameters / setting combinations prior to the first treatment and later, the second treatment.

- Following the test spot, wait to ensure that the chosen parameters indeed lead to the appropriate immediate response.

- If slight erythema and edema and no adverse events occurred, treatment should be continued using the same setting or increase by not higher than ~10% parameters for each session.
- If no results are observed, the treatment parameters should be increased.
- If the patient has experienced adverse events along with improvement, the treatment parameters should be decreased.
- Fine-tuning of the parameters can be done before proceeding to treat the entire sub-area with the chosen parameters. Modification of parameters per treated area within a treatment session should only be carried out if required due to safety concerns.

Assessment of the test spot will be performed following at least 2 hours and up to 48 hours depending on skin type. As such, the first treatment may be conducted on the same day as screening. It is important to not start treatment prior to full evaluation of the reaction to the test spot and having optimal parameters identified.

Table 1 - Test spot and treatment parameter chart

Starting parameters			
Skin Type	Mild	Moderate	Intense
I-II	220v / 30ms	250v / 15ms	280v / 15ms
III-IV	220v / 15ms	240v / 15ms	240v / 30ms
V-VI	220v / 10ms	230v / 5ms	240v / 5ms

Test Spots Mild			
Skin Type	Mild spot 1	Mild spot 2	Mild spot 3
I-II	220v / 5ms	220v / 15ms	220v / 30ms
III-IV	220v / 5ms	220v / 10ms	220v / 15ms
V-VI	220v / 5ms	220v / 8ms	220v / 10ms

Test Spots Moderate			
Skin Type	Moderate spot 1	Moderate spot 2	Moderate spot 3
I-II	250v / 5ms	250v / 10ms	250v / 15ms
III-IV	240v / 5ms	240v / 10ms	240v / 15ms

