12. SAFETY ASSESSMENT

Adverse Events Definitions

In this study, an Adverse Event (AE) is any undesirable clinical occurrence (sign, symptom, illness, or other medical event), that appears or worsens during the clinical study, or requires medical treatment or intervention to a subject, whether it is considered to be device related or not. If an adverse event occurs, the first concern will be the safety and welfare of the subject. Appropriate medical intervention will be made.

Any AE or complication reported by the subject or observed by the physician that occurs during or after treatment with the device will be recorded in the subject's medical record or source document and on the Adverse Event Case Report Form. The investigator will determine if the AEs are device related or procedure related. This assessment shall include the onset date, resolution date, severity, seriousness, frequency, treatment and outcome.

Each AE should be assessed according to the following criteria:

Severity

Each AE should be assessed for its severity, or the intensity of an event experienced by the subject.

Mild: Awareness of a sign or symptom that does not interfere with the subject's activity or is transient resolved without treatment and has no sequelae.

Moderate: May interfere with the subject's usual activity and require additional intervention and/or treatment, and may have additional sequelae.

Severe: Significant discomfort to the subject and/or interferes with the subject's activity. Additional intervention and or treatment are necessary. Additional sequelae occur. Severe is used to describe the intensity of an event experienced by the subject.

Adverse Device Effect (ADE)

Each AE should be assessed for its relationship to the device or procedure as identified as follows:

Device: This category should be restricted to adverse events directly attributable to the effect of the device.

Procedure: A procedure is any activity that supports the usage of the device.

Use the following categories for assigning the certainty of the relatedness:

Related: The AE is known to occur with the study agent, there is a reasonable possibility that the study agent caused the AE, or there is a temporal relationship between the study agent and event. Reasonable possibility means that there is evidence to suggest a causal relationship between the study agent and the AE.

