14. STATISTICAL CONSIDERATIONS

Statistical Design

This study is a randomized, open-label, multi-centre study.

Sample Size

Enrollment will continue until up to 100 evaluable subjects have been recruited to the study. Any subject removed from the study in accordance with the provisions of this protocol will be replaced by other subject.

Statistical Methods

All subjects who received any amount of treatment will be included in the report. The primary outcome measure is the subject's overall tolerability of the adjuvant combination treatment as compared to the standard of care post fractional RF treatment. The self-assessment will be based on a 5-point Likert scale - Subject Tolerability Scale (Appendix A). Summary statistics will be generated for subject tolerability immediately after treatment, 24 hours and 72 hours following

treatment as per the terms: Very tolerable, tolerable, having no opinion, intolerable and very intolerable.

The secondary outcomes measures are the subject's degree of discomfort and/or pain as measured by the visual analogue scale (VAS), the incidence of spontaneous adverse events (AEs) and the investigator's assessment of improvement using the Fitzpatrick Wrinkle and Elastosis Scale scores before and after treatment as well as Global Aesthetic Improvement Scale (GAIS) for each subject. VAS scores from the treated group will be compared with the VAS scores of the standard of care group. The investigator's assessment of improvement using the Fitzpatrick Wrinkle and Elastosis Scale from the treatment group will be compared with that of the standard of care group. The GAIS scores for both groups will also be compared.

Summary statistics will also be generated for all treatment emergent adverse events (TEAs). The following types will be reported:

- Overall TEAEs
- Severe TEAEs
- TEAEs related to treatment
- Serious Adverse Events (SAEs)
- SAEs related to treatment
- TEAEs leading to treatment discontinuation

15. DATA HANDLING and RECORD KEEPING

Confidentiality

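### Scheduled adverse event collection begins at the first treatment, so subjects barred after RF test spots have no AE form, no follow-up call and no clear place in the safety report

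*Combined protocol and SAP*

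**What the plan says.** Section 11.1 states that "up to three test spots will be performed on the area adjacent to the ear". These are device applications after consent, with voltages and pulse durations set out in Table 1. The reaction is then read: "Assessment of the test spot will be performed following at least 2 hours and up to 48 hours depending on skin type". The same section says how settings change if adverse events occur, so events at this step are expected.

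Tolerating the test spot is inclusion criterion 4 in Section 9, and Section 11.2 repeats the filter: "Subjects that did not experience significant pain or skin sensitivity in response to the test spots can receive treatments".

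In the Section 1 schedule, the row "Adverse Events / Concomitant Medications" is marked at Tx 1, Tx 2 and FU1 and is blank in the Screening & Test Spot column. The Section 11.1 procedure list includes concomitant medications but no AE assessment.

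Two rules turn on the word treatment. Section 12 provides that any AE or complication "that occurs during or after treatment with the device will be recorded" in the source and on the AE case report form. Section 14 states: "All subjects who received any amount of treatment will be included in the report".

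**The concern.** The filter selects on the reaction to the device. Subjects who react worst to RF energy are the ones who leave, and they leave before the first scheduled AE review, telephone call or questionnaire. A burn or pigment change that develops at a test spot after the reading has no planned contact at which it would be found.

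Incidence of AEs is a named secondary outcome in Section 7. If subjects exposed only to test spots are neither asked about events nor counted, the account of what the device did to everyone it was used on is incomplete, and the denominator depends on how one word is read.

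**Working it through.** The plan gives no figure to reproduce on this point. The check is a comparison of sections, followed by one illustration of scale.

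**1. Is the test spot a full-strength exposure?** In Table 1, compare test spot 3 with the starting treatment parameters, by skin type and intensity:

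| Skin type | Mild: start / spot 3 | Moderate: start / spot 3 | Intense: start / spot 3 |
|---|---|---|---|
| I-II | 220v 30ms / 220v 30ms | 250v 15ms / 250v 15ms | 280v 15ms / 280v 15ms |
| III-IV | 220v 15ms / 220v 15ms | 240v 15ms / 240v 15ms | 240v 30ms / 240v 30ms |
| V-VI | 220v 10ms / 220v 10ms | 230v 5ms / 230v 5ms | 240v 5ms / 240v 5ms |

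All 9 cells agree. The area is small, but the setting is the starting treatment setting.

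**2. Which AE contacts does a barred subject reach?**

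- Day 0: no AE mark in Section 1 and no AE item in Section 11.1.
- Spot assessment at 2 to 48 hours: yes, but no AE form is attached to it.
- Pre-treatment review at Tx 1 ("Review any changes in medication, health status or AE from last visit"): this covers the test-spot interval, but only for subjects who attend a treatment visit.
- Telephone calls (Sections 1 and 11.2): timed only from the two treatments.
- Early-termination visit (Section 11.3): doubtful. Section 11.2 describes enrolment and scheduling after the filter, and the Section 11.3 questions concern the second treatment.
- Screening log (Section 9): an entry only.

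So the spot assessment is the one certain contact.

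**3. Can that contact come too early?** Section 12 lists minor swelling for up to a week, and rarely burns and pigment change. Appendix B describes scabs forming at 24 to 72 hours and shedding 1 to 2 days later, that is, between 24 + 24 = 48 hours and 72 + 48 = 120 hours. Appendix B describes ordinary healing after full treatment, so it shows only how long the skin response runs. A reading at 2 hours, or even at 48, can precede the end of that course.

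**4. Are these subjects in the report?** Section 14 counts any amount of treatment. Section 1 lists the test spot and treatment as separate rows. The natural reading excludes subjects who had test spots only, but the plan does not say so. Section 12 is also uneven: its case report form rule refers to treatment with the device, while its rule on anticipated events refers to use of the device, which does reach a test spot.

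**5. Scale.** Let *f* be the proportion of tested subjects who are barred (assumed, since the documents give no rate). With 100 going on to treatment, the number barred is 100 × *f* / (1 − *f*):

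- *f* = 2%: 100 × 0.02 / 0.98 = 2.0
- *f* = 10%: 100 × 0.10 / 0.90 = 11.1

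**The case against.** The strongest reply is that AE duties do not depend on the schedule. Section 12 defines an AE as anything that appears or worsens during the study. It requires anticipated events at any time during or after use of the device to be reported to the sponsor, and its list includes burns and pigment change. All serious events must be reported, with no restriction to treated subjects. Section 13 provides for follow-up of on-going events up to 30 days after study completion. The test spot also has its own assessment.

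All of this stands, and it limits the point to *scheduled* collection. It does not close the gap. After the spot reading there is no visit, call or form, so a later event is known only if a subject who has already been screened out volunteers it.

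Four stronger readings are tempting, and the documents do not support them:

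- *Serious events will be under-reported in the tables.* The serious-event rule in Section 12 covers everyone.
- *The report excludes these subjects.* That is an inference, since Section 14 does not define whether a test spot counts as treatment.
- *Test-spot events in subjects who proceed cannot be told apart from later ones.* Section 12 requires an onset date, and the spots are beside the ear on the side of the neck while treatment is facial. What is missing is a stated rule for using this information.
- *The arm comparison is biased.* Test-spot failures occur before randomised treatment is assigned, so their omission cannot favour either arm.

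**Conclusion.** The concern holds in a limited form. A subject who receives RF energy at up to the starting treatment setting and is barred for the reaction has one assessment at 2 to 48 hours and no scheduled AE recording or contact afterwards. Whether that subject appears in the safety report rests on an undefined word.

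The consequence is incomplete device safety data and weak follow-up of exposed subjects. The randomised comparison of the topical combination with standard of care is unaffected. The figure of about 2 to 11 subjects per 100 treated rests wholly on the assumed 2% to 10% failure rate. No effect on event rates can be calculated, because the documents give neither a failure rate nor an expected event rate. The change is worth making because it is cheap and concerns people exposed by a study procedure.

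**What to change.** 1. Section 1: mark AEs in the Screening & Test Spot column, from the first test spot. Section 11.1: add AE assessment to the procedure list and tie the spot reading to the AE form.
2. Section 12: base the case report form rule on use of the device, to match the rule on anticipated events.
3. For subjects who fail the test spot, make the Appendix C call at 24 and 72 hours after it, and follow on-going events as in Section 13. An event that first appears after 72 hours would still depend on the subject reporting it.
4. Section 14: state that AEs in all test-spot-exposed subjects, treated or not, go in a separate listing with the number exposed. Keep events with onset before the randomised post-RF step out of the by-arm treatment-emergent tables unless they worsen afterwards.

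The cost is two short calls per failed subject, one case report form page and one listing. The reported device event count may rise slightly. No device setting or eligibility rule changes.

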Key Inclusion Criteria	
 • Male or non-pregnant, non-nursing female at least 21 years of age and less than 75 years of age. • Undergoing a dermatological procedure requiring ablation and resurfacing of the facial skin utilizing the Venus Viva™ SR system.
Key Exclusion Criteria	
 • Superficial metal or other implants in the treatment area. • Tattoos, permanent makeup, scars or piercings in the treatment area. • Any active condition in the treatment area, such as sores, psoriasis, eczema and rash.

	
 Any surgical procedure in the treatment area within the last three months or before complete healing.
Primary endpoint	The primary end point will be the tolerability of the application of the stem cell recovery complex (SCR Complex™) and a botanical lipid based occlusive (Bio Cel™) as compared with standard of care immediately following fractional RF treatments.
Secondary endpoints	The secondary outcomes will be the subject's degree of discomfort and/or pain as measured by the visual analogue scale (VAS), the incidence of spontaneous adverse events (AEs) and the investigator's assessment of improvement using the Fitzpatrick Wrinkle and Elastosis Scale scores before and after treatment as well as the Global Aesthetic Improvement Scale (GAIS) for each subject.
Statistical Methodology	
All subjects who received any amount of treatment will be included in the report. The primary outcome measure is the subject's overall tolerability of the adjuvant combination treatment as compared to the standard of care post fractional RF treatment. The self-assessment will be based on a 5-point Likert scale - Subject Tolerability Scale (Appendix A). Summary statistics will be generated for subject tolerability immediately after treatment, 24 hours and 72 hours following treatment as per the terms: Very tolerable, tolerable, having no opinion, intolerable and very intolerable.
 
Summary statistics will also be generated to present the degree of discomfort and/or pain following the procedure, all treatment emergent adverse events (TEAs) and the GAIS scores for the treatment group and standard of care group.

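### On the order listed in Section 11.2 both VAS readings precede that session's randomised topical step, so the Section 14 VAS comparison cannot show the adjuvant's same-session effect on discomfort

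*Combined protocol and SAP*

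**What the plan says.** Section 11.2 lists what happens after the RF pass. The first item is "Subject Discomfort Assessment recorded on a 100mm visual analogue scale (VAS) immediately post treatment". The second is the Subject Tolerability Scale, also immediate. The third is the randomised step: "Subjects will receive either the adjuvant combination treatment (SCR Complex™ followed by Bio Cel™ occlusive gel applied to the treatment area) or SOC". The third item has no time and no word such as before or after.

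The Schedule of Events marks the VAS at Tx 1 and Tx 2 only. It does not appear at the follow-up visit or in the telephone-call footnotes, and the Synopsis gives the same timing. Discomfort on the VAS is a secondary endpoint (Section 7).

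Section 14 then states: "VAS scores from the treated group will be compared with the VAS scores of the standard of care group". It names no visit or time point.

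Other text can be read as putting the topical first. The Synopsis frames the primary endpoint "as compared with standard of care immediately following fractional RF treatments". Section 14 speaks of "overall tolerability of the adjuvant combination treatment as compared to the standard of care post fractional RF treatment" and adds "Summary statistics will be generated for subject tolerability immediately after treatment, 24 hours and 72 hours following" treatment, which would make most sense if the product were already on the skin at time 0.

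Sections 3 and 10.2 credit Bio Cel with analgesic properties. Section 8 defines SOC as no topical for 24 hours, after which both arms resume the same skin care.

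**The concern.** A between-arm comparison tells us about the adjuvant only if the score is taken after the adjuvant has had a chance to act. If sites follow the list as printed, each VAS describes the RF pass and is complete before the arms differ in that session. A null result could then be reported as no effect on discomfort when the effect was not measured. A difference, if one appeared, would have to come from chance, carry-over, expectation in an open-label study, or unequal use of topical anaesthetic.

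If the two centres adopt different orders, the pooled VAS mixes two quantities. Nor can a reader tell whether the Tx 1 score may serve as a baseline.

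**Working it through.** The plan gives no alpha, SD, effect size, power or allocation ratio for the VAS, so there is no figure to reproduce. The main check is of the text.

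**Step 1: count the readings.** There are two VAS readings (Tx 1, Tx 2) and six tolerability scores (time 0, 24 h and 72 h after each of two treatments).

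| Order at time 0 | VAS after a same-session application | Tolerability scores after a same-session application |
|---|---|---|
| Score first (as listed) | 0 of 2 | 6 − 2 = 4 of 6 |
| Topical first | 2 of 2 | 6 of 6 |

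On either order, 0 of 2 VAS readings are later than immediate.

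**Step 2: what each reading can contain on the listed order.**
- Tx 1: no adjuvant has yet been applied, so the expected product effect is zero.
- Tx 2: only carry-over from Tx 1. The Schedule's day numbers give 21 − 7 = 14 days; Section 11.2 says three weeks, or 21 days. These two intervals need reconciling. Footnote 1 of the Schedule allows screening and Tx 1 on one day, which would give 21 days if Tx 1 falls on day 0.

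**Step 3: what the score can contain on the other order.** It captures the first moments after application. No passage gives a time course for pain or an onset time for Bio Cel. The only time course nearby concerns swelling: "The edema usually appears 1-2 minutes post-treatment and reaches its peak (of up to moderate edema) within 30 minutes". That shows the skin reaction is still developing at an immediate score, but it does not describe pain.

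**Step 4: look for a later discomfort score.** The Appendix C questionnaire is used in calls at 24 h and 72 h after Tx 1 and 24 h after Tx 2, and at the follow-up visit. It has yes/no and free-text items and no scale. The home form (Appendix A) rates tolerability of the procedure, not discomfort.

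**Step 5: illustration of size.** These inputs are assumptions, not in the documents: 50 per arm, two-sided 5%, SD 25 mm, full effect 15 mm, and a share f of that effect present when the score is taken. Ignoring the negligible opposite tail, power ≈ Φ(f × 15 / (25 × √(2/50)) − 1.96) = Φ(3f − 1.96).
- f = 1: Φ(1.04) = 85%
- f = 0.5: Φ(−0.46) = 32%
- f = 0.25: Φ(−1.21) = 11%
- f = 0 (Tx 1 on the listed order): 5%, the false-positive rate

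Over SDs of 20 to 30 mm and full effects of 10 to 15 mm, power is 39% to 96% with the full effect and 6% to 15% with a quarter of it.

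**Step 6: why the order decides the role of the Tx 1 score.** Take a full effect d = 0.566 SD (80% power unadjusted at 50 per arm) and adjust a later VAS for centre and the Tx 1 immediate score (100 − 4 = 96 df), with correlation ρ = 0.5.
- Pre-topical baseline: the effective effect is d/√(1 − ρ²) = 0.566/0.866 = 0.654, power 90%.
- Post-topical baseline that already carries the full effect: d(1 − ρ)/√(1 − ρ²) = 0.283/0.866 = 0.327, power 37%.

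**The case against.** The strongest reply is that the VAS is a secondary measure of pain from the RF procedure, that the Synopsis promises only summary statistics for it, and that the primary scale already has 24-hour and 72-hour scores after both treatments. Most of this stands, and it keeps the point away from the primary conclusion. But Section 14 does plan an arm comparison of the VAS, and a comparison of RF pain before the arms differ says nothing about the product.

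A second reply is that the bullets may not be a sequence, and that the Synopsis and Section 14 wording suggests the topical comes first. That is possible, and the conclusion is conditional for that reason.

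Three stronger readings are tempting, but the documents do not support them:
- A reader might infer that the VAS comparison is uninformative on either order. Without an onset time, and with analgesic properties claimed for Bio Cel, an early effect could be partly captured if the topical goes on first.
- A reader might infer from the parenthesis in Section 11.2, which places assignment after the first treatment visit, that the Tx 1 score precedes randomisation. That item sits under the pre-treatment heading, Section 8 assigns by subject number, and Section 11.1 gives each subject an identifying number at screening. The texts need reconciling; they do not establish late assignment.
- A reader might infer that the primary outcome is compromised. Only its time-0 score shares the ordering gap.

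**Conclusion.** The point holds, conditionally on the order. If sites follow the list, neither VAS reading can show a same-session adjuvant effect: Tx 1 has none to show and Tx 2 has at most carry-over from two to three weeks before. If the topical goes on first, the comparison is limited to the first moments of exposure. In both cases no discomfort score falls later in the 24 hours during which Section 8 has the arms differ in topical care.

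This is worth correcting before enrolment. It affects a secondary endpoint and leaves the 24-hour and 72-hour tolerability scores as they are. The conclusion rests on the text alone; the power figures only illustrate it and depend on assumed values.

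**What to change.** 1. **Section 11.2:** state whether the immediate VAS and time-0 Tolerability Scale come before or after the topical step, identically at both centres. Reconcile the parenthesis on assignment with its pre-treatment heading and with assignment by subject number in Section 8.
2. **Appendix A, Sections 1, 11.2 and 14:** add a 24-hour VAS line to the existing home form after each treatment. Base the between-arm VAS comparison on it, as a difference in mm with a 95% CI, shown by session.
3. **Role of the immediate VAS:** if it is pre-topical, use the Tx 1 score as a baseline covariate and do not read its arm difference as an adjuvant effect. If it is post-topical, keep it as an outcome and do not use it as a baseline.
4. **Topical anaesthetic:** Section 11.2 lists it after assignment and has its use recorded in the CRF. Report that use by arm, since it could itself create a VAS difference.
5. **Optional:** a clinic VAS at a fixed time after the topical step, at the same clock time in SOC.

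Items 1 to 4 cost one more home-form entry and a few sentences, with no added visit or subjects. Item 5 would add clinic time.

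Precision for one session, assuming 50 per arm, a pre-topical baseline with correlation 0.5 and adjustment for centre: the 95% half-width is 1.985 × SD × √(2/50) × √0.75, or 5.2, 6.9 and 8.6 mm for SDs of 15, 20 and 25 mm.

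Two limits remain. The new score is still open label, so a difference can include expectation, and the report should say so. Discomfort may also be near zero by 24 hours, since Section 12 expects irritation and redness to last minutes to hours, though minor swelling may last up to a week. In a simulation with latent SD 20 mm, a shift of 11.3 mm, scores cut at 0 and no baseline adjustment, power was about 76%, 60%, 46% and 28% when the SOC mean was about 22, 8, 4 and 2 mm.
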